Monkeypox is a viral zoonotic infection meaning that it can spread from animals to humans. It can also spread through human-to-human contact. The PALM-007 study will be conducted in the Democratic Republic of the Congo (DRC) to assess the efficacy and safety of tecovirimat, a potential treatment drug for Monkeypox in hospitalized patients. Given their proximity to the patient, PALM-007 personnel and staff associated with the study are at high risk of contracting Monkeypox disease. Therefore, there is a need to protect them by vaccination as recommended by the World Health Organization (WHO). (1)

The MVA-BN vaccine, which can be given subcutaneously (2), has been approved by regulatory authorities in the USA (JYNNEOS)(3) and Europe (Imvanex)(4) for prevention of Monkeypox infection..

The Ministry of Health, having given temporary authorization for the use of this vaccine, believes it is important to monitor vaccinated individuals and thus determine the safety profile of this vaccine in the Congolese adult population. This vaccination will therefore be accompanied by a safety follow-up of all participants.

Potential benefits

Data available to date suggest that MVA-BN vaccine is highly effective in the prevention of Monkeypox and has been approved by the US Food and Drug Administration (FDA) and European Medicines Agency (EMA).

A study on macaques has shown that 2 doses of MVA-BN induce 100% protection against a lethal challenge of aerosolized Monkeypox virus(5). A separate study in cynomolgus macaques demonstrated no significant difference between levels of neutralizing antibodies in animals vaccinated with ACAM2000 (a second-generation smallpox vaccine) and those vaccinated with 2 doses of MVA-BN(6). Preclinical studies and Phase I/II clinical trials of MVA-BN have suggested that 2 doses of vaccine are immunogenic generating antibody levels considered protective against smallpox and, by extrapolation, against monkeypox as well.(7)

In the DRC, the MVA-BN vaccine has received temporary authorization for use. Therefore, PALM-007 staff may benefit from participation in this study, in the form of protection against Monkeypox infection.

Possible risks

Like any active product, the MVA-BN vaccine can cause side effects. Data from several clinical trials show that MVA-BN has a favorable adverse effect profile. There are, however, some common mild adverse events (AEs), such as local site reactions and flu-like symptoms. Other local side effects may include erythema, pain, edema, pruritus, hyperpigmentation and induration. Other systemic side effects can include fatigue, headache, myalgias, nausea, chills, fever. The frequency of AEs, especially local site reactions, in people who have never been vaccinated against smallpox and vaccinated for the first time (with MVA-BN) does not appear to be significantly higher than the frequency of AEs in those who have previously been vaccinated.

2. Objectives of the study

2.1. General objective

The overall objective of this observational study is to monitor and assess the safety profile of the MVA-BN vaccine among staff and study personnel of the PALM-007 study in DRC.

2.2. Specific objectives

The specific objectives are as follows:

- Estimate the incidence of serious adverse events (SAEs) in all individuals vaccinated with the MVA-BN vaccine
- Estimate the incidence of AEs after each dose of MVA-BN vaccine.

3. Methods

3.1. Study design

This is a study of the safety of the MVA-BN vaccine through a one-arm prospective observational cohort study that will be conducted under the coordination of the National Pharmacovigilance Center of the DRC. After informed consent is obtained, study participants

will receive two doses of vaccine and will be actively followed up to the 28th days after their last dose of MVA-BN vaccine.

3.2. Study population

Participants 18 years and older will be recruited from personnel of the PALM-007 Monkeypox study and staff associated with the study in the DRC. Participation in the study will be voluntary and up to 1000 participants may be enrolled at the PALM-007 study sites or in Kinshasa.

3.2.1. Inclusion criteria

- Provides written informed consent
- 18 years of age or older
- At high risk for Monkeypox infections
- Personnel and staff associated with the PALM 007-Monkeypox study sites in the DRC
- Willingness and ability to communicate AEs to study personnel.

3.2.2. Exclusion criteria

- Allergy to MVA-BN or any of its components
- Pregnant or breastfeeding women
- Fever (axillary temperature $\geq 37.5^{\circ}\text{celsius}$)
- People who have already received the MVA-BN vaccine (in routine vaccination or another study involving this vaccine)
- Participants who, in the judgement of the investigator, will be at significantly increased risk as a result of participation in the study
- Individuals with any condition or circumstance that would render them unable to comply with study procedures (e.g., not reachable by phone)

3.4 Withdrawal from the study

Participants will have the right to withdraw from the study for any reason at any time. This will not affect their staff position on the PALM-007 study. People who have had a serious allergic reaction to the first dose of MVA-BN will not receive a second study dose but will be followed as described in section 4.2. If participants had a previous serious allergic reaction to any of the components of MVA-BN prior to joining this study, they may be at increased risk of serious allergic reactions. Therefore, these participants will be excluded from the study.

If a participant develops monkeypox infection, he/she will be withdrawn from the study and will receive the best treatment available for this disease. If this occurs between the first and second dose of vaccine, the participant will not receive the second dose.

If a participant decides to withdraw from the study, no further data will be collected about him/her. However, data collected up to the time of withdrawal will be used in analyses.

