4.1. Screening and enrollment of participants

All personnel and staff of the PALM-007 study will be offered the opportunity to participate in the study by reviewing and signing the informed consent. After signing informed consent, participants will be examined. The following parameters will be assessed:

- Anthropometric measurements (weight, height)
- Vital signs: temperature (axillary), blood pressure, heart rate and respiratory rate
- Medical history, including history of orthopox virus disease, vaccination, current co-morbidities and medication(s)
- Physical examination

- Pregnancy test will be done for all women of childbearing potential.

If a participant has met all eligibility criteria, they will be enrolled and will receive the vaccine as specified below. Participants who are excluded because of fever can be rescreened and included after resolution of the fever and its cause.

Enrolled participants will receive the MVA-BN vaccine by subcutaneous injection of 0.5 mL in the shoulder (left or right). Care must be taken to hold the skin well between 3 fingers and insert the needle at an angle of approximately 45°.

The first dose will be administered at the time of enrollment and the second dose 28 days later.

After each vaccination the participant will remain under observation for 30 minutes. All AEs occurring during this period of observation, will be recorded, and reported to the National Center for Pharmacovigilance and to the ethics committee according to Congolese regulations.

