4.2. Follow-up of participants

Participants will be followed until 28 days after the second dose of vaccine. Follow-up visit will be done either in person at INRB (in Kinshasa) and at the Monkeypox treatment centers in the PALM-007 study or by phone calls on Day 3, Day 14, and Day 28 post each vaccination. Study participants will be provided with contact information of vaccine research staff and have the right to contact the research team either directly or by phone if they have any questions about post-vaccination reactions they may be experiencing or if they are concerned. There is a window of +/- one day for each visit except the day of the second dose which can be done on day 28 after the first dose with a window of +7 days. This second dose must not be given before day 28. During each visit, participants will be asked to report to the research team AEs via open-ended questions. All SAEs will be followed-up. SAEs that have not resolved by the end of the per-protocol follow-up period for the subject (Day 28 after second dose) are to be followed until final outcome is known (to the degree permitted by the IRB-approved informed consent form). If it is not possible to obtain a final outcome for an SAE (e.g., the participant is lost to follow-up), the last known status and the reason a final outcome could not be obtained will be recorded by the investigator on an SAE report update and the CRF.

On the day of administration of the second dose of vaccine, vital signs, and physical examination will be done to all participants and a pregnancy test will be done on all women

of childbearing potential prior to vaccine administration. If the pregnancy test is positive, the second dose will not be given, and the participant will be followed up as described in [section 3.5](#). Participants will be instructed to report any AEs that are experienced outside of the protocol defined follow up days. The reporting form of the national pharmacovigilance system of the DRC will be used for reporting. The research team will complete the notification form which will be sent to the National Pharmacovigilance Center (CNPV) by e-mail (scanned copies).

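### Section 3.4 withholds dose 2 for a reaction to dose 1 only if it is a serious allergic one; other suspected vaccine-related SAEs have no rule and no stated investigator discretion

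*Combined protocol and SAP*

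**What the plan says.** Two doses are the stated course. Under section 3.1 of the protocol, participants "will receive two doses of vaccine and will be actively followed up to the 28th days after their last dose", and section 4.1 adds: "The first dose will be administered at the time of enrollment and the second dose 28 days later".

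Three exceptions are written:
- Serious allergic reaction (3.4): "People who have had a serious allergic reaction to the first dose of MVA-BN will not receive a second study dose". Such participants stay in follow-up under 4.2.
- Monkeypox infection (3.4): "If this occurs between the first and second dose of vaccine, the participant will not receive the second dose". The participant is also withdrawn.
- Pregnancy (4.2): "If the pregnancy test is positive, the second dose will not be given". Follow-up then runs under 3.5.

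Separately, section 3.4 gives the participant a way out: "Participants will have the right to withdraw from the study for any reason at any time". After withdrawal, no more data are collected.

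Investigator judgement of risk appears once, among the exclusion criteria in 3.2.2: "Participants who, in the judgement of the investigator, will be at significantly increased risk as a result of participation in the study".

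At the dose 2 visit, 4.2 requires a clinical check: "On the day of administration of the second dose of vaccine, vital signs, and physical examination will be done to all participants". Table 9.1 adds an assessment of AEs and SAEs and a medication review at that visit. Of all these checks, only the pregnancy test has a stated consequence for dosing.

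**The concern.** The protocol already accepts that a serious reaction to dose 1 can rule out dose 2, but limits this to allergic reactions and gives no reason for the limit. A life-threatening event or a hospitalization after dose 1 that is not allergic, but may well be due to the vaccine, meets the SAE definition in 4.3.1 and fits none of the three exceptions.

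What is at stake is mainly the safety of the participant who would be re-exposed. An investigator who withholds dose 2 is acting on a power the protocol does not state, and one who gives it is following the schedule. Sites may therefore decide differently, in a study whose overall objective is to monitor safety and whose first specific objective is the incidence of SAEs.

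**Working it through.** **1. Each event after dose 1, with its written consequence**

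| Event | Dose 2 | What follows |
|---|---|---|
| Serious allergic reaction (3.4) | withheld | follow-up under 4.2 |
| Monkeypox infection (3.4) | withheld | withdrawn from the study and treated |
| Positive pregnancy test (4.2) | withheld | follow-up under 3.5 |
| Participant withdraws (3.4) | not given | no further data |
| Non-allergic SAE, suspected related | nothing stated; the schedule in 3.1 and 4.1 stands | SAE followed to outcome (4.2), graded (4.3.2), reported (4.3.3) |
| Fever on the dose 2 day | nothing stated | nothing stated |

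The last two rows are the gap. The fifth is the point of substance and the sixth a clarification.

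**2. Does another provision fill the fifth row?**

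- *Risk criterion in 3.2.2.* Section 4.1 applies the eligibility criteria before enrollment and dose 1. Table 9.1 has one mark for eligibility assessment, in the screening column, and none at the dose 2 visit. Nothing says the criterion is applied again.
- *Checks at the dose 2 visit.* AEs and SAEs are assessed, so the team giving the dose knows the history. No action is attached to what they find.
- *SAE follow-up and reporting (4.2, 4.3.3).* Neither section asks anyone to decide on dose 2.
- *Withdrawal (3.4).* This is the participant's choice, not a medical stop. It also works against the study: 4.2 wants every SAE followed until its outcome is known, whereas withdrawal stops data collection. The visible text describes no route for declining dose 2 while staying in the study.

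**3. The fever row**

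Section 3.2.2 excludes people with an axillary temperature of 37.5 °C or above, and 4.1 lets them be rescreened once the fever and its cause resolve. For dose 2, temperature is measured among the vital signs, but no threshold or deferral is stated.

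**4. How often could this arise?**

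The documents give no rate of vaccine-related SAEs, so the rate p after dose 1 is an assumption. With n = 1000 (section 8), the expected number of cases is 1000p, and the chance of at least one is 1 − (1 − p)^1000:

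- p = 0.05%: 0.5 expected; 1 − 0.9995^1000 = 39%
- p = 0.1%: 1 expected; 1 − 0.999^1000 = 63%
- p = 0.5%: 5 expected; 1 − 0.995^1000 = 99%

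Over this assumed range the situation is rare for any one participant, but it could plausibly arise at least once. Not all such SAEs would be non-allergic, so these figures are upper values for the uncovered group.

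**5. Does any stated precision figure move?**

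The sample size section states a half-width of at most 0.05 with 1000 participants. The largest Clopper-Pearson half-width at n = 1000 occurs at 500 events: (0.5315 − 0.4685)/2 = 0.0315, so the statement is true. The bound is already met with 402 participants. Withholding dose 2 from a handful leaves it met.

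**The case against.** The strongest reply is that nothing here orders re-dosing. Section 3.1 is a design summary and 4.1 a schedule, and 3.4 does not call its exceptions exhaustive. Section 3.1 follows participants to 28 days after their last dose, which leaves room for a single dose. Section 6 binds the study to the Declaration of Helsinki and Good Clinical Practice, and the dosing team reviews AEs and SAEs at the visit. Consent pages are not visible and may contain wording on stopping.

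Much of this stands. A reader might infer that investigators would in fact give dose 2 after a related SAE; the documents do not show that. What remains is that three specific exceptions are listed, only one of them concerns a reaction, and the visible text states no general power to withhold.

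Three other stronger readings also go too far:

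- *The 7-day and 15-day reporting limits in 4.3.3 let dose 2 be given before anyone reviews the SAE.* The clock starts when a member of the research team becomes aware, so the site knows first. The limits are maxima for notifying outside bodies, and none of those bodies is given a dosing decision.
- *The per-dose SAE and AE estimates would be materially biased.* Any shift depends on numbers and recurrence rates that the documents do not give. If participants with any SAE are counted once, those with an SAE after dose 1 are already in the cumulative proportion.
- *Dose 2 must stop after every SAE that meets the adverse drug reaction definition in 4.3.1.* That definition covers any event whose relationship to the product cannot be excluded. An automatic stop could deny the second dose to high-risk staff after a coincidental illness, which is a debatable trade-off.

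**Conclusion.** The point holds as a gap in the written rule. The reaction-based stop for dose 2 is narrower than participant safety calls for, and no provision in the visible text gives the investigator discretion to go beyond it. This is more than missing detail, because literal adherence leads to the worse course: re-dosing, or a withdrawal that ends data collection.

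The size is small in numbers and cannot be fixed from the documents. That few participants would be affected is an assumption, consistent with the favorable adverse effect profile described in the background section. No stated precision figure changes. It is a cheap improvement, made for participant safety. The conclusion assumes that the removed consent pages contain no stopping provision.

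**What to change.** In section 3.4, after the serious-allergic-reaction rule, which stays as it is, add:

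> *Dose 2 is also withheld if, after an SAE or any other finding since dose 1, the investigator judges that a second dose would put the participant at significantly increased risk; an SAE the investigator considers related to the vaccine is a reason to withhold. The reason is recorded and the participant remains in follow-up as described in section 4.2.*

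In section 4.2, as a clarification, state that an axillary temperature of 37.5 °C or above on the dose 2 day defers the dose until the fever and its cause have resolved, within the existing Day 28 to Day 35 window.

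Table 9.1 needs no change, because the assessments are already scheduled at the dose 2 visit. The investigator must form and record a view on risk, and on relatedness where there has been an SAE. Sections 4.3.1 to 4.3.3 define an adverse drug reaction but assign no one to judge causality, so this is a small new task. The downside is that a few participants receive one dose, while the benefit described in the background section rests largely on two. Leaving the decision to documented judgement limits that loss.

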3.5 Pregnant and breastfeeding women

Available data on the risk of MVA-BN (JYNNEOS) vaccine on embryo-fetal and postnatal development is insufficient; therefore, pregnant and breastfeeding women will be excluded from the study. A pregnancy test will be performed at screening and on Day 28 for all women of childbearing potential. If a woman becomes pregnant following receipt of the vaccine, her pregnancy will be monitored. She will be followed up for the full duration of the pregnancy. She will follow antenatal visits in the health facilities and the schedule recommended by the national policy. She will be requested to communicate to the study staff all AEs for assessment and reporting purposes. The outcome and the pregnancy will be assessed: the newborn will be examined, and all malformation/birth defect reported as serious adverse event.

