4.3. Safety assessment

4.3.1. Definitions

Adverse event

An AE is any untoward or unfavorable medical occurrence in a human subject, including any abnormal sign (e.g., abnormal physical exam or laboratory finding), symptom, or disease, temporally associated with the subject's participation in the research, whether or not considered related to the research.

Adverse drug reaction

All noxious and unintended responses to a medicinal product. The phrase "responses to a "medicinal products" means that a causal relationship between the medicinal product and the adverse event is at least a reasonable possibility, i.e., the relationship cannot be ruled out.

Unexpected adverse event

Unexpected adverse event is an event whose nature, severity or outcome is not consistent with the applicable product information (investigator's brochure or package insert)

Serious adverse event

A serious adverse event is any untoward medical occurrence that:

- results in death,
- is life-threatening (places the subject at immediate risk of death from the event as it occurred),
- requires inpatient hospitalization or prolongation of existing hospitalization,
- results in persistent or significant disability/incapacity,
- is a congenital anomaly/birth defect or,

- is a medically important event.

NOTE: Medical and scientific judgment should be exercised. Events that significantly jeopardize the subject and/or require intervention to prevent one of the SAE outcomes listed above are generally considered medically important and are thus SAEs.

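### Section 3.4 withdraws participants who develop monkeypox, so scheduled safety contacts appear to end because of an adverse event, whereas allergic reaction and pregnancy stop dosing but keep follow-up

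*Combined protocol and SAP*

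**What the plan says.** On monkeypox, section 3.4 reads: "If a participant develops monkeypox infection, he/she will be withdrawn from the study and will receive the best treatment available for this disease". A further sentence bars the second dose if the infection falls between doses. Nothing is said about safety contacts after that withdrawal.

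Two other events after vaccination are handled differently:

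- **Serious allergic reaction to dose 1 (section 3.4).** The participant "will not receive a second study dose but will be followed as described in section 4.2".
- **Pregnancy (sections 3.5 and 4.2).** "If the pregnancy test is positive, the second dose will not be given, and the participant will be followed up" under section 3.5, where the plan adds: "She will be requested to communicate to the study staff all AEs for assessment and reporting purposes".

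Three further provisions bear on what data remain:

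- Section 3.4: "If a participant decides to withdraw from the study, no further data will be collected about him/her". Data gathered before withdrawal are used.
- Section 4.2: all SAEs are followed up, and "SAEs that have not resolved by the end of the per-protocol follow-up period for the subject" are followed to final outcome.
- Section 4.3.1: an adverse event includes any disease associated in time with participation, "whether or not considered related to the research".

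The first specific objective in section 2.2 is: "Estimate the incidence of serious adverse events (SAEs) in all individuals vaccinated with the MVA-BN vaccine". Section 8 plans proportions of participants with SAEs and AEs, with Clopper-Pearson 95% intervals, at 14 days after the first dose and 28 days after the second.

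**The concern.** Safety is the only objective of this study, and the cohort is enrolled because it is at high risk of monkeypox (section 3.2.1). An infection during follow-up is therefore foreseeable, and it counts as an adverse event. Making it a ground for withdrawal from the study means that follow-up ends because a safety event has occurred. Such loss is informative: the people who leave may well have a different risk of a later serious event, such as hospitalization, from those who stay.

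If scheduled contacts stop at diagnosis and the participant stays in the denominator, a later first SAE is counted as no event. The all-cause SAE proportion is then biased downward. Section 8 gives no rule for incomplete follow-up, and does not say how someone withdrawn before the second dose is counted at the time point 28 days after it.

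**Working it through.** **The plan's own figure.** Section 8 says that with 1000 participants the half-width of the 95% interval will not exceed 0.05. The Clopper-Pearson limits for x events in n are the 0.025 quantile of Beta(x, n−x+1) and the 0.975 quantile of Beta(x+1, n−x). Taking the widest interval over all x at n = 1000 gives a half-width of 0.0315, so the statement is true. At n = 990 it is 0.0316 and at n = 980 it is 0.0318. Losing a few participants does not matter for precision. The question is whether events are ascertained.

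**The text.**

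| Event after a dose | Second dose | Follow-up |
|---|---|---|
| Serious allergic reaction (3.4) | Not given | Kept, as in section 4.2 |
| Pregnancy found before dose 2 (3.5, 4.2) | Not given | Kept; all AEs requested |
| Monkeypox (3.4) | Not given if between doses | Withdrawn from study; nothing further stated |

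If withdrawal from the study meant only that vaccination stops, the separate sentence on the second dose would be redundant. The rule would also have no effect for someone infected after dose 2. The natural reading is that participation ends, including the Day 3, 14 and 28 contacts.

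**What can be lost.**

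- An infection that is already an SAE at withdrawal has been counted. It adds no bias to a per-participant SAE proportion.
- An SAE open at withdrawal is still followed.
- Exposed to loss are AEs that start after withdrawal, and first SAEs that start after withdrawal in participants whose infection was not yet serious.

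**Size.** Let N be the number vaccinated, x the SAEs observed, k the participants withdrawn for monkeypox, and r the share of those k with a first SAE after withdrawal that is not captured. Then:

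- observed proportion = x/N
- true proportion = (x + kr)/N
- bias = −kr/N

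N = 1000 comes from section 8. The documents give no x, k or r, so these are assumptions.

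- k = 0: bias is zero.
- k = 1: at most 1 missed, 1/1000 = 0.1 percentage point.
- k = 10, x = 2, r = 0.10 to 0.50: missed events are 10 × 0.10 = 1 to 10 × 0.50 = 5.

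| Case (k = 10) | Count | Proportion | 95% Clopper-Pearson |
|---|---|---|---|
| Observed | 2/1000 | 0.20% | 0.024% to 0.721% |
| True, r = 0.10 | 3/1000 | 0.30% | 0.062% to 0.874% |
| True, r = 0.50 | 7/1000 | 0.70% | 0.282% to 1.437% |

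The true proportion is then 3/2 = 1.5 to 7/2 = 3.5 times the reported one. Removing the 10 from the denominator does not repair this: 2/990 = 0.202%. The missing information is in the numerator.

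**The case against.** The strongest reply is that the harm is inferred. No sentence says that contacts stop after withdrawal for monkeypox. The bar on further data covers only a participant who decides to leave. Section 4.2 says in general terms that participants are followed to 28 days after the second dose, that all SAEs are followed up, and that participants are to report events between scheduled days. All of this is correct, and it is why the loss is called implied. It does not remove the problem: following known SAEs does not restore the contacts at which a new one would be elicited, and self-report depends on someone who has been told that he or she is no longer in the study.

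Second, the size rests wholly on assumed rates. Ten infections in 1000 vaccinated staff within about eight to nine weeks (28 + 28 = 56 days to 35 + 28 = 63 days) may be too many, and the intervals above overlap. At the first analysis time, only infections in the first 14 days can matter. This stands. The figures are an illustration, and the effect may be nil.

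Third, ending observation at infection could be a deliberate way to keep effects of the disease or its treatment out of the vaccine's safety profile. That would be coherent, but section 2.2 asks for SAE incidence in all vaccinated individuals and the plan states no such restriction. Separate tabulation keeps the two apart without discarding data.

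Fourth, the pregnancy comparison is looser than the allergic-reaction one, because section 3.5 describes antenatal follow-up and AE reporting, not the Day 3, 14 and 28 contacts by name. Also, the silence of section 8 on people who never receive the second dose applies to every reason for missing it. Both points are fair. The concern does not depend on either.

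**Conclusion.** The concern holds. As written, section 3.4 takes participants out of the study because of an adverse event, and nothing in the plan brings back the scheduled contacts. This conflicts with the objective in section 2.2, and with section 3.1, which plans active follow-up to 28 days after the last dose.

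The direction is known: if post-withdrawal SAEs are missed and the participants stay in the denominator, the SAE proportion is too low. The size is not known. It is zero without infections and at most 0.1 percentage point with one. It is 0.1 to 0.5 percentage point under the assumed 10 infections with 1 to 5 missed first SAEs, set against an assumed observed 0.2%. If SAEs are that rare, even a few missed events change the estimate appreciably. Stated precision is unaffected. The change should be made, with medium confidence, because the reading rests on implication and the rates are assumed.

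**What to change.** - **Section 3.4.** Reword so that participants who develop monkeypox stay in safety follow-up, by the visits or calls already scheduled, to 28 days after the last dose received, unless they choose to withdraw. Reconcile with section 4.2. Leave the treatment and second-dose rules as they are.
- **Section 8.** State that these participants count in the numerators and denominators of the AE and SAE proportions, including those who never received the second dose. Tabulate events with onset after monkeypox diagnosis separately.

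The cost is one amended sentence, one added sentence, and contacts that are already in the schedule and may be made by phone. The downside is small: some later events will reflect the disease or its treatment, which the separate table makes visible. No censored or time-to-event analysis is needed.
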